# 7.2.1 Hemagglutination Inhibition (HAI) Assay (Q Solutions and Other HAI Laboratories)

Hemagglutination inhibition testing will be conducted by  $Q^2$  Solutions using thawed frozen subject serum samples in a standardized and validated method with virus antigens produced in embryonated chicken eggs. Sera will be first treated to remove non-specific inhibitors of hemagglutination and then plated onto a microtiter well, starting with an initial dilution of 1:10 and followed by a series of 2-fold dilutions. The appropriate virus antigen and indicator erythrocyte suspension will be added to designated wells in 2 steps, with mixing and incubation at each step. The titration end-point will be taken as the highest dilution that demonstrates complete inhibition (100%) of hemagglutination. The serum HAI titer will be the geometric mean of triplicate test results. Based on new findings in a recent investigation concerning egg passage-induced point mutations in contemporary A(H3N2) strains [Zost 2017], testing (for at least H3N2 strains) will also be performed in a qualified assay using hemagglutinating antigens produced by recombinant methods capable of generating HA with and without specific egginduced mutations.

# 7.2.2 Microneutralization Assay (Novavax)

Nanoparticle Influenza Vacc	ine, Trivalent	Confidential	tNIV-E-101 Protocol
Novavax, Inc.	Version 2	5.0 – 13 November 2017	Page 51

The influenza virus microneutralization assay will be based on the WHO manual for the laboratory diagnosis and virological surveillance of influenza, with minor modifications [WHO 2011]. Briefly, subject test sera will be treated with receptor-destroying enzyme (RDE) and heat-inactivated at 56°C for 30 minutes. Sera will be prepared in 2-fold serial dilutions (starting from 1:10) in duplicates, in 96-well plates. Positive and negative virus controls and anti-influenza serum standards will also be included. An approximate tissue culture infective dose of 100 TCID50 will be added and incubated for 60 minutes at  $37^{\circ}C \pm 2^{\circ}C$  in 5.0%  $\pm 1\%$ CO2. After incubation, 100  $\mu$ L of trypsinized MDCK cells at a concentration of 1.5 x 10^5/mL will be added to each well and incubated for 18 to 22 hours at  $37^{\circ}C \pm 2^{\circ}C$  in  $5.0\% \pm 1\%$  CO2. On Day 2, plates will be fixed, blocked, and incubated with anti-influenza A nucleoprotein (NP) monoclonal antibody pool (1:1 of MAB8257 and MAB8258, Millipore Billerica, MA), followed by washing and incubation with a peroxidase-conjugated goat anti-mouse IgG (Kirkegaard and Perry Laboratories, Gaithersburg, MD). Finally, plates will be washed and incubated with 3,3',5,5'-tetramethylbenzidine substrate (Sigma) and the optical density (OD) will be read after adding the stop solution. A 4-parameter fit (SoftMax Pro software) will use the following equation to determine the OD value at which 50% of the MDCK cells are infected:

X = [(average OD of virus control wells) - (average OD of cell control wells)] / 2

All values  $\leq X$  will be deemed positive for neutralization activity.

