# 1.4 Nanoparticle Influenza Vaccine, Trivalent (Tri-NIV)

Novavax's Tri-NIV is based on purified, recombinant, full-length HA that self-assembles into distinct nanoparticle structures of approximately 20 to 40 nm. A baculovirus/*Spodoptera frugiperda* (Sf9) insect cell system is used to clone and express recombinant influenza HAs from influenza strains recommended for the 2017 - 18 Northern Hemisphere influenza season: A/Michigan/45/2015 (H1N1); A/HongKong/4801/2014 (H3N2); and B/Brisbane/60/2008 [WHO 2017]. Sf9 insect cells produce recombinant, uncleaved, glycosylated HAs that

assemble into homo-oligomers as trimers. When purified, HA trimers form higher order structures composed of 2 to 9 or more trimers per nanoparticle.

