# 2.2 Secondary Objectives

- To describe the immunogenicity of Tri-NIV at 2 different doses, and the licensed comparator Fluzone HD (Sanofi Pasteur) based on hemagglutination inhibition (HAI) responses to at least 2 historic and/or drifted A virus strains (one H1N1 and one H3N2).
- To describe the immunogenicity of Tri-NIV at 2 different doses, and the licensed comparator Fluzone HD (Sanofi Pasteur), based on microneutralization (MN) responses to vaccine-homologous and historic and/or drifted influenza A strains, and the vaccine-homologous B/Victoria lineage strain, at Day 21 post-dosing.

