# 2.3 Exploratory Objectives

- To describe the immunogenicity of Tri-NIV at 2 different doses, and the licensed comparator Fluzone HD (Sanofi Pasteur), based on HAI and MN responses to a contemporary B/Yamagata lineage strain Day 21 post-dosing.
- To describe the immune response to Tri-NIV at 2 different doses, and the licensed comparator Fluzone HD (Sanofi Pasteur), as measured by competitive-binding assays using purified HA and broadly-neutralizing HA monoclonal antibodies of varying specificities on Days 0 and 21.

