# 3.2.2 Secondary Endpoints

- Antibody titers specific for the HA receptor binding domains of at least 2 historic and/or drifted A virus strains (one H1N1 and one H3N2) as measured by the HAI assay at Day 0 pre-dosing and Day 21 post-dosing. Derived/calculated endpoints based on these data will include:
  - Geometric mean titer (GMT) defined as the antilog of the mean of the log-transformed HAI titers for a given treatment group.
  - $\circ$  Geometric mean ratio (GMR) defined as the ratio of post-vaccination and pre-vaccination HAI GMTs within the same treatment group (designated as GMRPost/Pre).
  - Seroconversion rate (SCR) defined as the percentage of subjects with either a baseline HAI titer < 1:10 and a post-vaccination titer ≥ 1:40, or a baseline HAI titer ≥ 1:10 and a 4-fold increase in post-vaccination HAI titer relative to baseline.

  - Seroprotection rate (SPR) defined as the percentage of subjects with an HAI titer  $\geq 1:40$ .
- Neutralizing antibody titers specific for the virus strains included in Tri-NIV and the Fluzone HD comparator, as well as selected historical A virus strains, as measured by a microneutralization assay at Day 0 pre-dosing and Day 21 post-dosing. In view of the time-consuming nature of neutralization assays, these may be performed on an informative subset of subjects who are selected for this purpose at randomization. Derived/calculated endpoints based on these data will include:
  - Geometric mean titer (GMT) defined as the antilog of the mean of the log-transformed neutralizing titer for a given treatment group.
  - Geometric mean ratio (GMR) defined as the ratio of post-vaccination and pre-vaccination neutralizing GMTs within the same treatment group (designated as GMRPost/Pre).
  - Seroconversion rate (SCR) defined as the percentage of subjects with either a baseline neutralizing titer < 1:10 and a post-vaccination titer  $\ge$  1:40, or a baseline titer  $\ge$  1:10 and a 4-fold increase in post-vaccination titer relative to baseline.

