# 7.2 Serological Assessments of Immunogenicity

Immunogenicity assessments will be made on subject sera collected on Days 0 and 21. The primary measure of immunogenicity for the trial is HAI titers specific for the HA receptor binding domains of each of the virus strains included in Tri-NIV. The secondary and /exploratory variables of immunogenicity include HAI titers specific for the HA receptor binding domains of at least 2 historic A virus strains (one H1N1 and one H3N2), and a representative of the B/Yamagata lineage; and neutralizing antibody titers specific for the virus strains included in Tri-NIV and the Fluzone HD comparator, as well as selected historical strains and a B/Yamagata strain. In addition, exploratory measures of immunogenicity also include antibodies competitive with broadly-neutralizing monoclonal antibodies to HA of varying specificities, as measured by competitive-binding in a biosensor assay.

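### Protocol 7.2.2 names only an anti-influenza A stain for microneutralization, so the readout for the influenza B endpoints is not validly specified

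*Protocol*

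**What the plan says.** Protocol 1.4 lists the vaccine strains as "A/Michigan/45/2015 (H1N1); A/HongKong/4801/2014 (H3N2); and B/Brisbane/60/2008", that is, two type A strains and one type B strain.

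Protocol 2.2 sets a secondary MN objective for the A strains "and the vaccine-homologous B/Victoria lineage strain, at Day 21 post-dosing". Protocol 3.2.2 defines the endpoint as "Neutralizing antibody titers specific for the virus strains included in Tri-NIV and the Fluzone HD comparator", so it includes the B strain. Protocol 2.3 adds an exploratory objective "based on HAI and MN responses to a contemporary B/Yamagata lineage strain Day 21 post-dosing", and Protocol 7.2 repeats the neutralization scope "as well as selected historical strains and a B/Yamagata strain". The SAP carries the same B-strain MN scope in its objectives (2.1.2, 2.1.3) and endpoints (2.2.2, 2.2.3), and for B/Yamagata in its exploratory analyses (7.3).

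Protocol 7.2.2 gives the method. It opens with "The influenza virus microneutralization assay will be based on the WHO manual for the laboratory diagnosis and virological surveillance of influenza, with minor modifications" and presents what follows as a brief description. The detection step is "plates will be fixed, blocked, and incubated with anti-influenza A nucleoprotein (NP) monoclonal antibody pool", with a mixing ratio and catalogue numbers, followed by a peroxidase conjugate, substrate and an OD reading. The cut-off is "X = [(average OD of virus control wells) - (average OD of cell control wells)] / 2", and values at or below X count as neutralization. Positive and negative virus controls and serum standards are included, but no plate-acceptance criterion is given.

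**The concern.** The stain, the OD and the cut-off form one chain. If the stain does not mark cells infected with the challenge virus, an infected well looks like an uninfected one and the OD no longer measures neutralization. The only stain that either document names is labelled for influenza A, with no exception for B plates.

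At stake is the MN information on one of the three vaccine strains, a secondary endpoint, and the MN part of the cross-lineage B question. The Trial Rationale (Protocol 1.8) says that this question will be evaluated in humans. If invalid B plates were reported, a flat result could be mistaken for similarity between Tri-NIV and Fluzone HD, or for absence of a cross-lineage response.

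**Working it through.** The plan gives no figure to reproduce here. The check sets the method against the endpoints and then follows the plan's cut-off rule.

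**1. Required against specified**

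| Virus on plate | MN titer required | Detection reagent stated |
|---|---|---|
| H1N1 and H3N2 (homologous, historic or drifted) | Yes, secondary | Anti-influenza A NP pool |
| B/Brisbane/60/2008 (Victoria) | Yes, secondary | None for type B |
| B/Yamagata strain | Yes, exploratory | None for type B |

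The SAP fills no gap: it describes no assay, and its secondary analysis section (7.2) lists HAI only.

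**2. Number of titers.** Protocol 3.2.2 allows MN to be run on a subset of unstated size. If all 330 or so subjects were tested on Days 0 and 21 against both B strains, the upper limit is about 330 × 2 × 2 = 1,320 titers.

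**3. Cut-off with no cross-reaction (assumption).** Let VC and CC be the mean ODs of the virus-control and cell-control wells.

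- X = (VC − CC)/2.
- If B-infected cells do not stain, VC ≈ CC, so X ≈ 0.
- A well with positive background OD is above X, so no well counts as neutralized and every titer is below 1:10.
- Protocol 10.4.1.2 then assigns the value 5. GMT = 5 on both days, GMR = 5/5 = 1, and SCR = 0% because no titer reaches 1:40 or rises 4-fold. This would hold in every group.

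If background were subtracted before comparison, both X and the wells would lie near 0 and the calls would be noise. The uniform result is therefore one possible outcome, not the only one.

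**4. Cut-off with partial cross-reaction (assumption).** Let S be the full staining signal above background and f the fraction of S obtained on B-infected cells.

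- VC = CC + fS, so X = fS/2.
- A fully neutralized well has OD = CC. It is called positive only if CC ≤ fS/2, that is, f ≥ 2·CC/S.
- The documents give no ODs. For assumed CC of 0.05 to 0.2 and S of 1 to 2:
  - lowest threshold: 2 × 0.05/2 = 0.05;
  - highest threshold: 2 × 0.2/1 = 0.40.

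Under these assumptions the pool would need 5% to 40% of its full signal before even a completely neutralized B well could be called positive. The documents give no cross-reactivity data to place f in or outside that range.

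**The case against.** The strongest reply is that 7.2.2 is a summary of a cited manual. It names no challenge virus for any strain, so strain-specific materials are plainly not all listed, and a B reagent may stand in a laboratory procedure that is not among these documents. This stands in part. It rules out the inference, which a reader might draw, that the B-strain MN objectives cannot be met at all. It does not make the text right. The section goes down to catalogue numbers and gives no B exception, although the protocol writes strain-specific steps elsewhere: H3N2 testing in 7.2.1 and an extra B-strain purification step in 4.2.2.

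Second, the documents never say that the pool fails on influenza B. That is correct; it is an assumption drawn from the label.

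Third, the controls in 7.2.2 would probably expose the fault, since the virus-control wells would resemble the cell-control wells and a B serum standard would not titrate. This stands as a mitigating factor, though no stated criterion stops such a plate from being reported. A reader might infer that GMT 5 and SCR 0% will appear in the study report; that needs the OD assumptions above and controls that nobody acts on.

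Fourth, a reader might think that the B-strain evaluation as a whole is lost. It is not: HAI covers B/Brisbane as a primary endpoint and B/Yamagata as an exploratory one. Sera may be archived for up to 25 years for repeat assays (Protocol 7.3), and the trial is descriptive.

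**Conclusion.** The point holds as a mis-specified assay step. As written, 7.2.2 applies a type A stain to plates that must yield type B titers, and the cut-off built on that stain would have no valid signal if the pool does not adequately detect influenza B. The affected part is the MN result for B/Brisbane (secondary) and B/Yamagata (exploratory), in all three groups. The conclusion rests on the reagent's label; the all-negative outcome rests further on zero cross-reaction, positive background OD and no background subtraction. A-strain MN and all HAI endpoints are untouched, and the error is recoverable from stored sera. It should be corrected before any B-strain MN titer is reported.

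**What to change.** In Protocol 7.2.2:

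- Limit the anti-influenza A NP pool to H1N1 and H3N2 plates.
- State the detection antibody or other readout used on B plates, and that it is suitable for both the Victoria and Yamagata lineages.
- Require a minimum virus-control minus cell-control OD before titers from a plate are reported. The value should come from the laboratory's own assay data, since the documents give none.

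If no suitable B readout is available, restrict the MN objectives, endpoints and analyses to A strains in the protocol (Synopsis, 2.2, 2.3, 3.2.2, 3.2.3, 7.2) and the SAP (2.1.2, 2.1.3, 2.2.2, 2.2.3, 7.3), and leave the B strains to HAI.

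If a B reagent is already in the laboratory procedure, naming it takes about one sentence, with a further line for the acceptance criterion. If not, the cost is a reagent and the work to show that it performs on both lineages. No extra subjects, visits or blood are needed in either case.

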#### 10.4.1.2 Immunogenicity

The immunogenicity analysis will be based on the PP population. A separate ITT population analysis will not be produced unless > 10% of at least 1 treatment group is excluded from the PP population. HAI antibody titers specific for each of the vaccine-homologous, historical and/or drifted, and cross-lineage virus strains tested, will be summarized by treatment group based on the following parameters (with 95% CIs):

- 1) Geometric mean titer (GMT) at baseline (screening) and post-vaccination on Day 21. Samples with no detectable HAI activity at the lowest dilution (1:10) will be assigned a value of 5 for calculation.
- 2) GMR the ratio of the post-vaccination GMT on Day 21 to the baseline (Day 0) value.
- 3) Seroconversion rate (SCR) defined as the percentage of subjects with either a baseline HAI titer < 1:10 and a post-vaccination titer ≥ 1:40, or a baseline HAI titer ≥ 1:10 and a 4-fold increase on Day 21 in post-vaccination HAI titer relative to baseline.

- Seroprotection rate (SPR) defined as the percentage of subjects with an HAI titer ≥ 1:40 at a given time-point.

Neutralizing antibody titers specific for each of the virus strains will be summarized by treatment group for each virus stain tested based on the following parameters (with 95% CIs):

- 1) GMT at baseline (screening) and post-vaccination on Day 21. Samples with no detectable neutralizing activity at the lowest dilution (1:10) will be assigned a value of 5 for calculation.
- 2) GMR the ratio of the post-vaccination GMT on Day 21 to the baseline (Day 0) value.
- 3) SCR defined as the percentage of subjects with either a baseline neutralizing titer < 1:10 and a post-vaccination titer  $\geq$  1:40, or a baseline titer  $\geq$  1:10 and a 4-fold increase on Day 21 in post-vaccination titer relative to baseline.

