2.2.2 Secondary Endpoints

- Antibody titers specific for the HA receptor binding domains of at least 2 historic and/or drifted A virus strains (one H1N1 and one H3N2) as measured by the HAI assay. Derived/calculated endpoints based on these data will include:
 - \circ Geometric mean titer (GMT) defined as the antilog of the mean of the log-transformed HAI titers for a given treatment group.
 - \circ Geometric mean ratio (GMR) defined as the ratio of post-vaccination and pre-vaccination HAI GMTs within the same treatment group (designated as GMR_{Post/Pre}).
 - Seroconversion rate (SCR) defined as the percentage of subjects with either a baseline HAI titer < 1:10 and a post-vaccination titer ≥ 1:40, or a baseline HAI titer ≥ 1:10 and a 4-fold increase in post-vaccination HAI titer relative to baseline.
 - Seroprotection rate (SPR) defined as the percentage of subjects with an HAI titer ≥ 1:40.
- Neutralizing antibody titers specific for the virus strains included in Tri-NIV and the Fluzone HD comparator, as well as selected historical A strains, as measured by a microneutralization assay at Day 0 pre-dosing and Day 21 post-dosing. In view of the time-consuming nature of neutralization assays, these may be performed on an informative subset of subjects who are selected for this purpose at randomization. Derived/calculated endpoints based on these data will include:
 - \circ Geometric mean titer (GMT) defined as the antilog of the mean of the log-transformed neutralizing titer for a given treatment group.

- \circ Geometric mean ratio (GMR) defined as the ratio of post-vaccination and pre-vaccination neutralizing GMTs within the same treatment group (designated as GMR_{Post/Pre}).
- Seroconversion rate (SCR) defined as the percentage of subjects with either a baseline neutralizing titer < 1:10 and a post-vaccination titer \ge 1:40, or a baseline titer \ge 1:10 and a 4-fold increase in post-vaccination titer relative to baseline.

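### The microneutralization cut-off printed in Protocol 7.2.2 is the 50% infection point only on background-corrected ODs, and neither document states that correction

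*Protocol*

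**What the plan says.** Protocol 7.2.2 gives a short account of the MN assay, based on a cited WHO manual with modifications that it does not list.

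- Plate set-up: "Sera will be prepared in 2-fold serial dilutions (starting from 1:10) in duplicates, in 96-well plates".
- Reading: "the optical density (OD) will be read after adding the stop solution".
- Purpose of the equation, used with a 4-parameter fit: "to determine the OD value at which 50% of the MDCK cells are infected".
- The equation: "X = [(average OD of virus control wells) - (average OD of cell control wells)] / 2".
- Decision rule: values at or below X "will be deemed positive for neutralization activity".

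No blanking or background subtraction is described between the reading and the decision rule.

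The SAP does not add one. SAP 2.2.2 names neutralizing titers "as measured by a microneutralization assay at Day 0 pre-dosing and Day 21 post-dosing" without describing the assay. SAP 7.2 covers HAI only, and SAP 12 gives only the rule for values below the LLoQ.

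The titers feed GMT, GMR and seroconversion rate (SCR) as secondary endpoints. Seroconversion in Protocol 3.2.2 starts from "either a baseline neutralizing titer < 1:10 and a post-vaccination titer" of at least 1:40; otherwise it needs a 4-fold rise from a baseline of at least 1:10. Protocol 10.4.1.2 sets the floor: "Samples with no detectable neutralizing activity at the lowest dilution (1:10) will be assigned a value of 5 for calculation". Neutralizing titers to B/Yamagata are exploratory, and SAP 7.3 analyzes them with the primary immunogenicity methods.

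**The concern.** Uninfected cells usually give some OD signal, and the formula acknowledges this by using the cell-control wells. Halving the difference between the two controls gives half of the signal above background. It does not give the OD midway between the controls unless the background is added back. If X is compared with ODs as read, the rule demands more than 50% neutralization and scores some qualifying wells as negative.

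At stake are the absolute MN GMTs, the number of samples at the below-1:10 floor, and seroconversion near the 1:40 limit. Protocol 1.8 rests its case for protection against drifted strains on 50% MN titers in ferrets, so the human assay should deliver the 50% titer that its description promises. Protocol 7.3 also allows the same assays to be repeated on archived sera, which could carry an ambiguous cut-off into later comparisons.

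**Working it through.** **Inputs.** From Protocol 7.2.2: the printed X, its stated 50% meaning, and the rule that values at or below X are positive. Assumption: OD is linear in the infected share p, so OD = CC + p(VC - CC). The documents give no OD values, background levels or curve slopes.

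**Step 1: when the printed X has its stated meaning.** Subtract CC from each well. At p = 0.5 the corrected OD is (VC - CC)/2, which is the printed X. Example with VC = 2.0 and CC = 0.10: a well at the midpoint reads 1.05, its corrected value is 1.05 - 0.10 = 0.95, and X = (2.0 - 0.10)/2 = 0.95. The formula is then exact. The same holds if plates are blanked on the cell controls, or if CC = 0.

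**Step 2: ODs as read.** At p = 0.5, OD = CC + (VC - CC)/2 = (VC + CC)/2. The printed X is (VC - CC)/2, so the difference is CC.

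**Step 3: infected share at the printed X, on ODs as read.** Share f = (X - CC)/(VC - CC) = 0.5 - CC/(VC - CC). This is below 0.5 whenever CC > 0. If VC < 3CC, X falls below the cell-control OD itself, and even a fully neutralized well would fail. For example, VC = 0.8 and CC = 0.3 give X = 0.25.

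**Step 4: illustrative effect on titer.** For a symmetric dose-response curve of slope h, the titer read at X divided by the 50% titer is k = (f/(1 - f))^(1/h). All ODs and slopes below are assumed.

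| VC | CC | Printed X | Midpoint | Share at X | k, h = 1 | k, h = 2 |
|---|---|---|---|---|---|---|
| 2.0 | 0.04 | 0.98 | 1.02 | 0.480 | 0.922 | 0.960 |
| 2.0 | 0.10 | 0.95 | 1.05 | 0.447 | 0.810 | 0.900 |
| 2.0 | 0.20 | 0.90 | 1.10 | 0.389 | 0.636 | 0.798 |
| 1.0 | 0.30 | 0.35 | 0.65 | 0.071 | 0.077 | 0.277 |

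In the first three rows titers read at 0.64 to 0.96 of the 50% titer, or 0.06 to 0.65 of one 2-fold step (-log2 k). The last row has high background and shows that this range is not a bound.

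**Step 5: what cancels.** A factor k common to all samples drops out of between-group GMT ratios, and out of post/pre ratios when both titers are above the floor. It stays in absolute GMTs and can push low titers below 1:10, where they become 5.

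Seroconversion depends on how titers are read, which the text does not say. If each titer is the highest positive 2-fold dilution and k = 0.90, SCR can move either way:

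- True titers 21 and 79 should read 20 and 40, a 2-fold rise (not seroconverted). They become 18.9 and 71.1, which read 10 and 40 (seroconverted).
- True titers 15 and 42 should read 10 and 40 (seroconverted). They become 13.5 and 37.8, which read 10 and 20 (not seroconverted).

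These pairs were chosen to show what is possible. They say nothing about frequency.

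**The case against.** The strongest reply is that Protocol 7.2.2 never says that X is compared with uncorrected ODs. The formula already subtracts the cell-control signal, and on a corrected scale it is right. The account is openly a summary of a cited method, and the laboratory procedure and software set-up are not in the documents. On this view the text omits a step and contains no error. That stands in part: nothing here shows that the laboratory computes titers wrongly. It does not clear the text, because the protocol prints an exact formula, attaches a 50% property to it and gives a decision rule. The only reading step it mentions is the OD after the stop solution. Taken together, these do not deliver 50% without an unstated correction.

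Three further objections stand:

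- The 50% point coincides with the OD midpoint only under the linearity assumption.
- All titer and seroconversion figures rest on assumed ODs and slopes. The discrete reading is also assumed, and the 4-parameter fit may mean that titers are interpolated.
- The MN endpoints are secondary or exploratory, and testing may be limited to a subset.

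A reader might infer that the trial's MN titers will be too low, or that the comparison with Fluzone HD is biased. The documents support neither. The correction may already be made, and one rule applied to all groups largely cancels between them.

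In the other direction, a reader might take Protocol 10.5, which says that no hypothesis tests are specified, to mean that no test can be touched. SAP 7.1 plans a chi-square p-value for the SCR difference, SAP 7.3 carries the primary methods over to B/Yamagata neutralizing titers, and SAP 12 sets 0.05 as the significance level.

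**Conclusion.** The cut-off is wrong as written if it is applied to ODs as read, and right on a background-corrected scale that neither document mentions. Under linearity the discrepancy in X is exactly CC. Its effect on titers cannot be determined from the documents, and the figures above are illustrations only.

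The point touches the secondary MN endpoints (GMT, GMR, SCR) and the exploratory B/Yamagata MN endpoint. Any effect would fall mainly on absolute titers, the below-1:10 floor and the 1:40 limit. Primary HAI does not use X. The text should be corrected, but this is not evidence of faulty laboratory data. Confidence is medium, because the laboratory procedure may already settle the matter.

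**What to change.** Check the laboratory procedure, then make the text match it in one of two ways:

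- Write X = (VC - CC)/2 + CC, where VC and CC are the mean ODs of the virus-control and cell-control wells, and apply it to ODs as read.
- Keep the printed X and state that the mean cell-control OD is subtracted from every serum well before comparison with X.

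The cost is one line of assay wording. Design, visits, sample size and the primary HAI analysis do not change.
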